# 5.3 Sample size

We chose a convenience sample of 250 women based on the following: Stanford Gynecology clinic has approximately 10,000 unique visits per year. A "worst case" HPV prevalence rate of 5% (similar to rural Thailand), yields approximately 500 positives for HR-HPV per year and recruitment experiences from similar studies indicates a recruitment rate of 50% of the positives for something like this is feasible. In fact, the local HPV prevalence rate in our catchment area is likely much higher than 5%. Also 250 women would allow for adequate precision of 95% relative to agreement of the menstrual specimen with the lab-generated HPV result (alpha =.001, beta=.10).

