# 3.1 Study Enrollment

# For positive HR-HPV participants:

We plan to recruit patients from Stanford research IT Starr cohort tool to identify patients who have had a positive HR-HPV test in the last 18-months. We will then contact their provider to get permission to include them in the study before their next in-person follow up. This follow-up visit can be any time after positive HR-HPV result up to 18-months. This follow-up visit can be for a repeat cervical cancer screening pap test, colposcopy, or loop electrosurgical excision procedure. Patients identified who are HR-HPV positive will be contacted by their provider to broach the possibility of research participation to the patient. If this patient expresses interest in the project, the provider will ask if the research staff can then contact the patient. If the patient agrees, then the research staff will contact the patient. In addition, patient's with known positive HR-HPV results who present to the clinic for colposcopy or loop electrosurgical excision procedure will be approached by their provider during that clinic visit to see if the patient would be willing to participate in the project. If the patient agrees, then research staff will present the project in detail to the patient and obtain consent. Pre-procedure meetings (either in person or over the phone) will be performed with the subjects individually, where the process will be discussed and instructions on how to use the Q-pads and the vaginal swabs will be explained to ensure women fully understand the process. We will also hand out (or mail) instructions with pictures on paper to minimize any risk associated with using the devices. We do not anticipate any screen failures. Eligibility is based on standard of care testing.

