# For participants with no prior HR-HPV history:

We plan to recruit patients from Stanford Gynecology clinic. We will review the clinic schedule for patients presenting to the clinic for their routine well woman visit with cervical cancer screening. Their provider will approach the patient during that clinic visit to assess if the patient would be willing to participate in the project. If the patient agrees, then research staff will present the project in detail to the patient and obtain consent. At the time of the routine cervical cancer screening, additional study swabs will be collected. Prior to discharge, research staff will show the subject how to use the Q-pads and the vaginal swabs to ensure subjects fully understand the process. We do not anticipate any screen failures.

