#### 3.3 Enrollment

The target number of subjects at our gynecology clinic is 250 patients with or without previous HR-HPV diagnoses. We expect to complete this study within 12 months.

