# 5.0 STATISTICAL CONSIDERATIONS

#### 5.1 Outcome Measurements

Primary outcome is to compare the accuracy and percent analytic agreement of clinician and self-collected cervico-vaginal brush samples with Q-pad-collected menstrual blood for HR-HPV detection in women with and without previous positive HR-HPV results. The secondary outcome is to assess the ability to detect oncoproteins in Q-pad collected menstrual blood samples from women with ASCUS+ to determine the utility in cervical cancer/precancer detection and to test the utility of a low and high threshold HR-HPV reflex scheme to similarly increase the specificity of HR-HPV testing derived from menstrual blood. Neither outcome measures relate to safety.

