# **APPENDIX B: Protocol Summary of Changes**

Any administrative changes to the protocol including spelling corrections, minor clarifications, renumbering, and reformatting are not summarized in the following table.

Section	Change to Protocol	Rationale
Title Page	Date and version # changed	Changed due to this revision
Specific Study Aims	Added samples from women with no previous history of HR-HPV to specific aim #1	The study team assessed the funding timeline and the current sample (n=70) and the goal of n=250 and identified the need to expand the inclusion criteria. By including those without a history of HPV, we are able to better assess specificity and sensitivity. One challenge our team has faced is that far less women menstruate regularly than anticipated—this is largely due to contraceptive use.
Study Enrollment and Participant Eligibility	Created two groups for study enrollment to include women with no previous history of HR-HPV	To collect as much information as possible given funding timeline restraints. See above.
Study Enrollment and Participant Eligibility	Changed age restrictions to include for women over 45 years of age.	To allow for menstruating women over the age of 45 to participate. Upon review of our age eligibility, we saw no reason to exclude those over 45 years of age who menstruate. Screening still occurs in this population.
Material and Methods	Changed methods to include approaching women presenting to clinic for repeat cervical cancer screening with or without a history of HR-HPV.	To expand enrollment.
Statistical Considerations	These changes will not impact the statistical methods.	To accommodate expanded enrollment.

Data Management	Added section 6.4	To provide clarity on
Considerations		amendment approval.

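### Accuracy is part of the primary outcome, but the analysis plan names no estimate of missed infections, and their precision depends on an uncontrolled number of HR-HPV positives

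*Combined protocol and SAP*

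**What the plan says.** Section 5.1 states: "Primary outcome is to compare the accuracy and percent analytic agreement of clinician and self-collected cervico-vaginal brush samples with Q-pad-collected menstrual blood". The comparison is to cover both groups of women, those who have tested positive before and those who have not. Specific Aim 1 says the same.

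Section 5.2 assesses agreement of the binary menstrual-blood result with the clinician swab and the self-swabs, using Cohen's kappa. It names no sensitivity, specificity, positive agreement, negative agreement or confidence limits.

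Section 5.3 calls 250 a convenience sample and supports it in two ways. The first is a feasibility chain: 10,000 visits at 5% prevalence "yields approximately 500 positives for HR-HPV per year and recruitment experiences from similar studies indicates a recruitment rate of 50% of the positives". The second is the statement that "250 women would allow for adequate precision of 95% relative to agreement of the menstrual specimen with the lab-generated HPV result (alpha =.001, beta=.10").

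Section 3.3 states: "The target number of subjects at our gynecology clinic is 250 patients with or without previous HR-HPV diagnoses". Sections 3.0 to 3.2 describe the two groups but give no split, cap or minimum number of positives. For the history group, section 3.1 says: "This follow-up visit can be any time after positive HR-HPV result up to 18-months". For the other group it says: "We will review the clinic schedule for patients presenting to the clinic for their routine well woman visit with cervical cancer screening".

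Appendix B gives the background to the second group: "The study team assessed the funding timeline and the current sample (n=70) and the goal of n=250". It adds: "By including those without a history of HPV, we are able to better assess specificity and sensitivity".

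**The concern.** For a screening device the main accuracy question is how many infections it misses. That estimate has the comparator-positive women as its denominator, not all 250. The feasibility chain in section 5.3 counts positives only, whereas the 250 in section 3.3 is a mixture whose composition nobody controls. The precision statement concerns overall agreement and does not carry over to positive agreement.

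The study could therefore finish as planned, with high overall agreement and a respectable kappa, and report nothing on missed infections. If positive agreement were then calculated afterwards, its limits could be much wider than a sample of 250 suggests.

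**Working it through.** **The plan's own figures.** The feasibility chain reproduces: 10,000 × 0.05 × 0.50 = 250, as a count of HR-HPV-positive women.

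The agreement statement cannot be reproduced, because no null value, expected value or sidedness is given. As one trial reading, take a two-sided one-sample test of a proportion with alternative p1 = 0.95, alpha 0.001 and power 0.90:

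n = [3.29·√(p0(1−p0)) + 1.28·√(p1(1−p1))]² / (p1−p0)²

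This gives 212, 250 or 301 for p0 = 0.85, 0.86 or 0.87. A matching null exists, but it is not in the documents, so the match confirms nothing. On any reading, the statement is about overall agreement.

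**Expected number of positives.**
- From the documents: 250 in total (3.3), 70 enrolled when the second group was added (Appendix B), 5% prevalence (5.3).
- Assumed: all 70 had a prior positive (inferred from the timing); a share h of them is still positive at sampling, with h = 30%, 50% or 70%; all 180 remaining places go to women with no history; prevalence q in that group is 5%, or 15% as an alternative.

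Positives = 70h + 180q

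| q | h = 30% | h = 50% | h = 70% |
|---|---|---|---|
| 5% | 21 + 9 = 30 | 35 + 9 = 44 | 49 + 9 = 58 |
| 15% | 21 + 27 = 48 | 35 + 27 = 62 | 49 + 27 = 76 |

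If instead all 180 places went to women with a recent positive, the count would be 250h, that is 75, 125 or 175.

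**Precision of positive agreement.** Wilson 95% limits, with z = 1.96 and p = 0.90:

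[p + z²/2n ± z·√(p(1−p)/n + z²/4n²)] / (1 + z²/n)

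| Positives n | 95% limits |
|---|---|
| 30 | 74.4% to 96.5% |
| 44 | 77.7% to 95.9% |
| 62 | 80.1% to 95.3% |
| 125 | 83.5% to 94.1% |

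In the no-history group alone at 5%, there are 180 × 0.05 = 9 expected positives. Detecting 8 of 9 has limits of 56.5% to 98.0%.

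**What overall agreement and kappa reveal.** Suppose 238 of 250 pairs agree (95.2%) and all 12 discordant pairs are missed infections. With P comparator positives, the Q-pad reads P − 12 positive. Chance agreement is pe = [P(P−12) + (250−P)(262−P)]/250², and kappa = (0.952 − pe)/(1 − pe).

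| P | Sensitivity | pe | Kappa |
|---|---|---|---|
| 30 | 18/30 = 60% | 0.825 | 0.73 |
| 125 | 113/125 = 90% | 0.500 | 0.90 |

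Overall agreement is identical in the two rows. Kappa moves in the right direction, but a kappa of 0.73 does not tell the reader that 40% of infections were missed.

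**The case against.** **Kappa already guards against a useless test.** A strip that always reads negative would agree in 171 of 180 no-history women (95.0%) at 5% prevalence, but its kappa is 0. In the full 250 with 30 positives it agrees in only 220/250 = 88%. This stands: a reader might infer that the plan could pass a worthless device, and its own statistic prevents that. What remains is narrower. Kappa responds to missed infections but does not estimate them.

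**The counts of positives are not the plan's.** This also stands. They depend on assumed persistence and on every remaining place going to women with no history. Section 5.3 presents 5% as a worst case and says local prevalence is probably much higher, without giving a figure. At an assumed 15% the range is 48 to 76. Nobody should conclude that the study will have only about 30 positives.

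**The second group may displace nobody.** Appendix B reports 70 women against a goal of 250 and says fewer women menstruate regularly than expected. If women with a recent positive are the limiting supply, the added women can only add positives. A reader might infer that the expansion harmed the study, or that a quota is needed. The documents support neither. A quota would be a trade-off, and its feasibility is in doubt.

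**Any analyst can read sensitivity from the two-by-two table.** True, and that makes the fix cheap. But accuracy is a named primary outcome, so its estimate, comparator and limits belong in section 5.2.

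**Conclusion.** The point holds as a gap between the primary outcome and the planned analysis. Accuracy is named in section 5.1, section 5.2 provides no estimate of it, and section 5.3 speaks to overall agreement only. With no group split, the precision for missed infections rests on an uncontrolled number of positives. Under the stated assumptions that number is 30 to 58 at 5% prevalence and 48 to 76 at 15%. Limits around 90% positive agreement then run from 74% to 97% at 30 positives and from 80% to 95% at 62.

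It would be tempting to go further and say that 250 is too small or that the alpha and beta calculation is wrong. The documents support neither claim. Section 5.3 sets no target for positive agreement against which 250 could fail, and the agreement calculation cannot be checked because its inputs are not stated.

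All these counts rest on the inference that the 70 were all prior positives, and on assumed positivity in both groups. Section 3.0 also defines the second group as having no previous history, whereas section 3.2 requires only no positive in the last 18 months. That adds uncertainty about its positivity.

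**What to change.** 1. **Section 5.2 (the main change).** Report positive and negative percent agreement of the Q-pad against the clinician swab, and likewise against the self-swab, each with its denominator and 95% limits. Do this overall and by prior-HPV group, beside kappa. State that no sensitivity conclusion will be drawn from the no-history group alone.
2. **Section 5.3.** Say that the positives chain shows recruitment feasibility only and that the precision statement concerns overall agreement. Add that the precision of positive agreement depends on the number of positives, and give expected limits over a stated range.
3. **Optional, only if recruitment of women with a recent positive allows it.** Monitor the number of clinician-swab positives and give women with a recent positive priority for the remaining places. Otherwise close at 250 and label positive agreement exploratory.

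Items 1 and 2 cost one extra table and a few sentences, with no additional women, samples or assays. The limits for positive agreement will be wider and look less favourable than those for overall agreement. Item 3 could slow recruitment.

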# 6.0 DATA MANAGEMENT CONSIDERATIONS

#### 6.1 Data management

REDCap will be used for data collection and measures taken to protect identifying

information when exporting data. A unique study ID will be used in all statistical analyses to protect confidentiality. All electronic devices used in data collection will be both encrypted and password protected through Stanford IRT.

Adverse Events, protocol deviations, aggregate data, and individual data will all be reviewed by the research team at monthly intervals or as necessary. The Principal Investigator, [name], with the help of the Family Planning Division Research Team will be responsible for Data and Safety Monitoring. Assessments of data and events captured by the monitoring will be performed on a continual bases, simultaneously with the reporting data from analysis sources (i.e. physician office visits, follow up phone calls). If there is an unanticipated problem (UP; unexpected, related to research, AND harmful), it will be promptly reported to the IRB. [name], as the Data Safety Monitoring person, will disseminate the outcome of all reviews to the IRB.

# 6.3 Confidentiality

Participants in the study will be seen in private rooms for enrollment. No PHI will be left on participant's voicemail and/or email. Prior to enrollment, participants will receive HIPAA training and will work to protect the privacy interests of participants. A PHI secure website application will be used for data collection and measures taken to protect identifying information when exporting data. A unique study ID will be used in all statistical analysis to protect confidentiality. All study personnel with direct access to subjects' medical records will take reasonable precautions within the constraints of applicable regulatory requirements to maintain the confidentiality of the subjects' identity.

# 6.4 **Protocol Review and Amendments**

The protocol, the proposed informed consent and all forms of participant information related to the study (e.g. advertisements used to recruit participants) will be reviewed and approved by the Stanford IRB and Stanford Cancer Center Scientific Review Committee (SRC). Any changes made to the protocol will be submitted as a modification and will be approved by the IRB prior to implementation. The Protocol Director will disseminate the protocol amendment information to all participating investigators.

## APPENDIX A: Participant Eligibility Checklist

Protocol Title:	Screening for Cervical Intraepithelial Neoplasia Using Self- Collected Menstrual Blood
Protocol Number:	47250
Principal Investigator:	[name]

#### **II. Subject Information:**

Subject Name/ID:	
Gender: Male	🔀 Female

#### **III. Study Information:**

 $\boxtimes$  SRC Approved  $\boxtimes$  IRB Approved  $\boxtimes$  Contract Signed

#### **IV. Inclusion/Exclusion Criteria**

Inclusion Criteria (From IRB approved protocol)	Yes	No	Supporting Documentation*
1. 18 years or older			
2. Menstruate regularly			
3. Comfortable using menstrual pads			
4. Comfortable using vaginal swabs			
5. Comfortable committing to using condoms from time of self-collection and provider collected sample			
Exclusion Criteria (From IRB approved protocol)			
1. Women younger than 18 years old			
2. Women who are post-menopausal or not menstruating regularly			

\*All subject files must include supporting documentation to confirm subject eligibility. The method of confirmation can include, but is not limited to, laboratory test results, radiology test results, subject self-report, and medical record review.

# **APPENDIX B: Protocol Summary of Changes**

Any administrative changes to the protocol including spelling corrections, minor clarifications, renumbering, and reformatting are not summarized in the following table.

Section	Change to Protocol	Rationale
Title Page	Date and version # changed	Changed due to this revision
Specific Study Aims	Added samples from women with no previous history of HR-HPV to specific aim #1	The study team assessed the funding timeline and the current sample (n=70) and the goal of n=250 and identified the need to expand the inclusion criteria. By including those without a history of HPV, we are able to better assess specificity and sensitivity. One challenge our team has faced is that far less women menstruate regularly than anticipated—this is largely due to contraceptive use.
Study Enrollment and Participant Eligibility	Created two groups for study enrollment to include women with no previous history of HR-HPV	To collect as much information as possible given funding timeline restraints. See above.
Study Enrollment and Participant Eligibility	Changed age restrictions to include for women over 45 years of age.	To allow for menstruating women over the age of 45 to participate. Upon review of our age eligibility, we saw no reason to exclude those over 45 years of age who menstruate. Screening still occurs in this population.
Material and Methods	Changed methods to include approaching women presenting to clinic for repeat cervical cancer screening with or without a history of HR-HPV.	To expand enrollment.
Statistical Considerations	These changes will not impact the statistical methods.	To accommodate expanded enrollment.

Data Management	Added section 6.4	To provide clarity on
Considerations		amendment approval.
